Exploratory: DNA sample (optional), inflammatory mediators, blood biomarker samples, and sputum samples

Statistical Analyses Approximately 250 subjects will be enrolled and randomized (1:1) to the VX-445/TEZ/IVA treatment arm or control arm (IVA or TEZ/IVA).

The primary efficacy endpoint is the absolute change in ppFEV₁ from baseline through Week 8

for the VX-445/TEZ/IVA group. The primary null hypothesis to be tested is that the mean absolute change in ppFEV₁ from baseline through Week 8 is 0 for the VX-445/TEZ/IVA treatment group. The null hypothesis will be tested at a 2-sided significance level of 0.05.

For the primary hypothesis, assuming a within-group SD of 7.0 percentage points and a 10% dropout rate at Week 8, a sample size of 125 subjects in the VX-445/TEZ/IVA arm will have >99% power to detect the within-group difference of 3.0 percentage points (1 sample *t*-test at a 2-sided significance level of 0.05).

The primary endpoint will be analyzed using a mixed-effects model for repeated measures (MMRM). The model will include the absolute change from baseline in ppFEV₁ at Day 15, Week 4, and Week 8 as the dependent variable; treatment group, visit, and treatment by visit as fixed effects; with continuous baseline ppFEV₁, continuous baseline SwCl, and comparator group (IVA comparator versus TEZ/IVA comparator) as covariates; and an unstructured covariance structure for the within-subject errors.

For the primary endpoint, the results obtained from the model will be the estimated within-treatment difference through Week 8 (average of Week 4 and Week 8) for the VX-445/TEZ/IVA group. The same model will be used to estimate between group differences (difference between VX-445/TEZ/IVA and the control group) through Week 8. The adjusted mean with a 2-sided 95% CI and a 2-sided *P* value will be provided for the primary endpoint and second key secondary endpoints.

The safety endpoints include AEs, clinical laboratory values, ECGs, vital signs, and pulse oximetry through completion of study participation. The safety analyses will be descriptive only.

IDMC Reviews An independent data monitoring committee (IDMC) will conduct safety reviews of study data as outlined in the IDMC charter.

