12.3.3.1 Analysis of Primary Efficacy Endpoint

The primary efficacy endpoint is the absolute change in ppFEV₁ from baseline through Week 8 for the VX-445/TEZ/IVA group. The primary endpoint will be analyzed using a mixed-effects model for repeated measures (MMRM). The model will include the absolute change from baseline in ppFEV₁ at Day 15, Week 4, and Week 8 as the dependent variable; treatment group, visit, and treatment by visit as fixed effects; with continuous baseline ppFEV₁, continuous baseline SwCl, and comparator group (IVA comparator versus TEZ/IVA comparator) as covariates; and an unstructured covariance structure for the within-subject errors. The Day 15 Visit will not be included in the estimation of the average treatment effect through Week 8. The model will be estimated using restricted maximum likelihood. Denominator degrees of freedom for the *F* test for fixed effects will be estimated using the Kenward-Roger approximation. An unstructured covariance structure will be used to model the within-subject errors. If the model estimation does not converge, a reduced compound symmetry covariance structure will be used instead. Conditional on the observed data and covariates, missing data due to treatment or study

discontinuation will be assumed to be missing at random; consequently, no imputation of missing data will be performed.

The primary results obtained from the model will be the estimated within-treatment difference through Week 8 (average of Week 4 and Week 8) for the VX-445/TEZ/IVA group. The adjusted mean with a 2-sided 95% CI and a 2-sided *P* value will be provided. Furthermore, the treatment difference at each post-baseline visit will also be provided, obtained from the model.

Sensitivity analyses for handling missing data will be described in the SAP.

Supportive analyses and subgroup analyses by selected baseline characteristics will also be described in the SAP.

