7.2 Sample Size and Power

The primary efficacy endpoint is the absolute change in ppFEV₁ from baseline through Week 8 for the ELX/TEZ/IVA group. The primary null hypothesis to be tested is that the mean absolute change in ppFEV₁ from baseline through Week 8 is 0 for the ELX/TEZ/IVA treatment group. The null hypothesis will be tested at a 2-sided significance level of 0.05.

For the primary hypothesis, assuming a within-group standard deviation (SD) of 7.0 percentage points and a 10% dropout rate at Week 8, a sample size of 125 subjects in the ELX/TEZ/IVA arm will have >99% power to detect the within group difference of 3.0 percentage points (1 sample t test at a 2-sided significance level of 0.05).

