9.3.1.2 Primary Analysis

The primary analysis will be performed using a mixed-effects model for repeated measures (MMRM) with the absolute change from baseline at Day 15, Week 4 and Week 8 as the dependent variable. The model will include treatment group, visit, and treatment-by-visit interaction as fixed effects, with continuous baseline ppFEV₁, continuous baseline SwCl, and comparator group (IVA comparator versus TEZ/IVA comparator) as covariates. The Day 15 Visit will not be included in the estimation of the average treatment effect through Week 8. The model will be estimated using restricted maximum likelihood. Denominator degrees of freedom for the *F*-test for fixed effects will be estimated using the Kenward-Roger approximation². An unstructured covariance structure will be used to model the within-subject errors. If the model estimation does not converge, a compound symmetry covariance structure will be used instead. Conditional on the observed data and covariates, missing data will be assumed to be missing at random; consequently, no imputation of missing data will be performed.

The primary results obtained from the model will be the estimated within-group treatment difference through Week 8 (average of Week 4 and Week 8) for the ELX/TEZ/IVA group. The adjusted means with 2-sided 95% confidence intervals and 2-sided *P* values will be provided. Furthermore, the within-group treatment difference at each post-baseline visit will also be provided, obtained from the model.

The adjusted mean (with SE) obtained from the MMRM analysis at each post-baseline visit up to Week 8 will be plotted by treatment group.

The primary analysis will be conducted with the clinic spirometry data only. An additional analysis may also be performed to include pooled spirometry data obtained in clinic and by Air Next Spirometer, if the Air Next Spirometry data are assessed to be reasonably consistent with clinic spirometry data.

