9.3.1.4 Sensitivity Analysis

MMRM based on Multiple Imputation (MI)

An underlying assumption of the MMRM method is that data are missing at random. To minimize the amount of missing data, subjects who prematurely discontinue study drug treatment will continue to complete all scheduled study visits for spirometry and other efficacy assessments.

To assess the impact of missing data and the assumption that data are missing at random, a multiple imputation algorithm will be used if at least 10% of the subjects have missing changes in ppFEV₁ at Week 8 in any treatment group. Missing absolute change from baseline in ppFEV₁ assessments will be imputed starting from the first visit with missing values, for which all subsequent visits through Week 8 are also missing. For intermediate missing data, i.e., missing values that fall between two non-missing ones, it is reasonable to assume that they are missing at random and therefore will not be imputed. An MMRM analogous to that for the primary analysis of the primary endpoint will be applied to each imputed dataset and the relevant MI estimators will be reported. Details for the MI steps are presented in [Appendix D](#).

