Appendix D: Steps for Multiple Imputation

For the multiple imputation (MI) to be applied to the MMRM model for the primary efficacy endpoint, the following steps will be followed:

Imputation distribution

The imputation distribution for the missing absolute change from baseline in ppFEV₁ at visit t will be a normal distribution. All randomized subjects will be classified into one of three categories based on the following rules:

- Non-missing category: Subjects who have a ppFEV₁ assessment at Week 8 (i.e., subjects who have a non-missing absolute change from baseline in ppFEV₁ at Week 8).
- Missing category 1: Subjects with missing absolute change from baseline in ppFEV₁ at Week 8, who discontinued treatment because of adverse events, noncompliance with study drug, death, or physician decision, or because the subject refused further dosing or required prohibited medication.
- Missing category 2: Subjects who discontinued treatment for any reason not listed in Category 1 and have missing absolute change from baseline in ppFEV₁ at Week 8, or subjects who have completed 8 weeks treatment duration but are missing the absolute change from baseline in ppFEV₁ at visit Week 8

Imputation algorithm

We will use the following algorithm that relates the mean of the missing absolute change from baseline in ppFEV₁ at visit t to the missing categories defined above. The algorithm will be implemented within each treatment group as follows:

- Missing category 1: randomly draw a sample from the normal distribution(μ_{25}, σ^2), where μ_{25} is the 25th percentile of the non-missing absolute changes from baseline in ppFEV₁ at visit t and σ^2 is the sample variance estimated using the non-missing absolute changes at visit t .
- Missing category 2: randomly draw a sample from the normal distribution(μ, σ^2), where μ is the mean of the non-missing absolute changes from baseline in ppFEV₁ at visit t and σ^2 is the sample variance estimated using the non-missing absolute changes at visit t .

Analysis model

The complete MI method is described below:

- Form an “imputed dataset” by imputing missing values at each visit for those subjects who have a missing value at the visit and have all subsequent values missing. The appropriate normal distribution specified in the algorithm above will be used for each such subject, based on their category.
- Repeat this process K ($K=20$) times to form K imputed datasets.

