- Fit the same MMRM model to each imputed dataset to estimate the absolute change at Week 8.
- Combine the results from the K imputed datasets using the SAS procedure MIANALYZE to derive the MI estimator.

Let θ be the true treatment difference. Denote by $\tilde{\theta}_k$ the estimate of θ from the k^{th} imputed dataset, and the corresponding estimate of the variance is denoted by \tilde{v}_k . The MI estimator of θ , $\tilde{\theta}_{\text{MI}}$, is the average of the K individual estimates.

The estimated variance of $\tilde{\theta}_{\text{MI}}$ is a combination of the between- and within-imputation variability as follows: $\tilde{v}_{\text{MI}} = \tilde{v} + \left(1 + \frac{1}{K}\right) \tilde{v}_w$, where $\tilde{v}_w = \frac{1}{K} \sum_{k=1}^K \tilde{v}_k$ is the within-imputation variability and is $\tilde{v} = \frac{1}{K-1} \sum_{k=1}^K (\tilde{\theta}_k - \tilde{\theta}_{\text{MI}})^2$ is the between-imputation variance. The statistic $T = \frac{\tilde{\theta}_{\text{MI}} - \theta}{\sqrt{\tilde{v}_{\text{MI}}}}$ has an approximate $t_{\tilde{v}}$ distribution, where $\tilde{v} = (K - 1) \left(1 + \frac{W}{B}\right)^2$.

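### The primary single-arm confidence interval comes from a two-arm MMRM whose covariance is not stated to be arm-specific, so its coverage is off if the arms differ in spread

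*SAP*

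**What the plan says.** The primary hypothesis is that the mean ppFEV₁ change in the ELX/TEZ/IVA arm is zero (SAP 7.2). The estimate is that arm's average of Week 4 and Week 8. It comes from an MMRM containing both arms, with treatment, visit and their interaction, baseline ppFEV₁, baseline sweat chloride and comparator group (Protocol 12.3.3.1; SAP 9.3.1.2). The first key secondary endpoint, within-arm sweat chloride, uses the same model (SAP 9.3.2.2).

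The covariance wording is:

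- SAP 9.3.1.2: "An unstructured covariance structure will be used to model the within-subject errors".
- Protocol synopsis: "and an unstructured covariance structure for the within-subject errors".
- Fallback in Protocol 12.3.3.1: "If the model estimation does not converge, a reduced compound symmetry covariance structure will be used instead".
- Fallback in SAP 9.3.1.2: "If the model estimation does not converge, a compound symmetry covariance structure will be used instead".

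None of these says whether the matrix is common to both arms or estimated by arm, and no robust standard error is named.

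SAP 9.3.1.3 rules out a supportive analysis of the primary endpoint. The one sensitivity analysis is multiple imputation, run only if at least 10% of an arm lacks a Week 8 value. It returns to the same model: "An MMRM analogous to that for the primary analysis of the primary endpoint will be applied to each imputed dataset" (SAP 9.3.1.4) and "Fit the same MMRM model to each imputed dataset to estimate the absolute change at Week 8" (Appendix D).

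**The concern.** An unstructured matrix leaves variances and correlations free across visits. It does not make them free across arms. Under one common matrix, the standard error of the ELX/TEZ/IVA mean borrows half its variance from the control arm. For a 1:1 difference between arms this does no harm, because the true variance of the difference depends on the sum of the two arms' variances. For one arm's mean it does harm. If the active arm is the more variable, the interval is too narrow; if control is, it is too wide.

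This trial makes single-arm means its primary and first key secondary results, so the point falls on the headline estimate. Equal spread is nowhere shown: the documents give one within-group SD (7.0), no control-arm SD and no sweat chloride SD. Two other parts of the plan work with the arm's own spread. The sample size is set "to detect the within group difference of 3.0 percentage points (1 sample t test" with that SD, and the imputation variances come from each arm separately: "The algorithm will be implemented within each treatment group as follows".

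**Working it through.** **Inputs from the documents.** Two-sided alpha 0.05; 125 subjects in the ELX/TEZ/IVA arm; 10% dropout; SD 7.0; difference 3.0 (SAP 7.2); 1:1 allocation of about 250 (Protocol 12.1). **Assumed:** control SD from 4 to 9.

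**1. The plan's own figure.** 125 less 10% is 112.5. With n = 112 the noncentrality is 3.0 × √112 / 7.0 = 4.54, and the one-sample t-test has power 99.4% (99.5% with n = 113). The stated figure of more than 99% reproduces.

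**2. Coverage by formula.** Take 112 per arm.

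- Pooled SD = √((49 + SDc²)/2), and r = pooled SD / 7.
- True standard error of the active mean = 7/√112 = 0.661.
- Coverage = 2Φ(t × r) − 1, with t = t(0.975; 222 df) = 1.971.
- Half-width = t × r × 0.661.
- From the arm's own SD: t(0.975; 111 df) × 0.661 = 1.982 × 0.661 = 1.31.

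Example with SDc = 4: pooled SD = √32.5 = 5.70; r = 0.814; t × r = 1.605; coverage 89.1%; half-width 1.06. That is 1.31 − 1.06 = 0.25 points too narrow.

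| Control SD | 4 | 5 | 6 | 7 | 8 | 9 |
|---|---|---|---|---|---|---|
| Coverage, common matrix (formula) | 89.1% | 91.3% | 93.4% | 95.1% | 96.6% | 97.7% |
| Half-width, common matrix (formula) | 1.06 | 1.13 | 1.21 | 1.30 | 1.40 | 1.50 |
| Coverage, common matrix (simulation) | 89.0% | 91.2% | 93.0% | 95.0% | 96.4% | 97.6% |
| Mean half-width, common matrix (simulation) | 1.02 | 1.09 | 1.17 | 1.26 | 1.35 | 1.45 |

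**3. Simulation of the planned model.** Settings: three visits, unstructured REML with Kenward-Roger, 125 per arm, monotone random dropout (6% missing at Week 4, 10% at Week 8), two continuous covariates plus comparator group, assumed between-visit correlation 0.7, and 3,000 replicates per SD. The Monte Carlo standard error of coverage is about 0.4 points (0.6 at SD 4). Half-widths are slightly below the formula's because dropouts contribute their earlier visits. Across the six control SDs:

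- by-arm matrix: coverage 94.5–95.2%, mean half-width 1.26–1.27, df 121–122 (242 with a common matrix);
- model fitted to the ELX/TEZ/IVA arm alone: coverage 94.6–95.4%, mean half-width 1.26–1.27;
- between-arm difference: coverage 94.8–96.2% (common) and 94.7–96.3% (by-arm).

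A second, separately coded simulation (2,500 runs per setting, fixed t quantile in place of Kenward-Roger) agrees. At control/active SD ratios of 0.7 and 1.25 the common matrix covers 91.7% and 97.0%, and the by-arm matrix 95.4% and 94.9%.

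**4. Effect on the decision.** Power at 3.0 points with a common matrix is about Φ((3.0 − half-width)/0.661): 99.8% at control SD 4, falling to 98.8% at control SD 9. The size of the test leaves 5% only if the mean change is zero and the spreads still differ. It would then be 100 − 89.1 = 10.9% at control SD 4 and 100 − 97.7 = 2.3% at control SD 9.

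**5. Sweat chloride.** With no SD given, only a ratio can be used: r = √((1 + ratio²)/2). Control/active ratios of 0.5, 0.8 and 1.25 give coverage of 88.1%, 92.6% and 97.4%.

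**The case against.** The case against is that the point is conditional and the documents contain nothing that triggers it. Every coverage figure away from 95% rests on an assumed control SD, and the 0.25-point error needs an SD of 4. At 6 to 8 the half-width is wrong by about 0.1 point, on a planned effect of 3.0. No decision changes at that effect. If the triple combination did nothing for anyone, randomised arms from a common on-treatment baseline would have equal spread, and the type I error would hold. The one-sample t-test is a planning simplification and Appendix D is a missing-data device, so neither commits the primary model to by-arm variances. By-arm SDs at each visit are already planned (SAP 9.3.5.1 with 9.1 for ppFEV₁; 9.3.2.2 for sweat chloride) and would expose unequal spread.

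Most of this stands as a limit on size. The SD range is an assumption, the harm is to the interval rather than the decision, and the t-test and imputation rule show only that the plan is at ease with arm-specific spread elsewhere. It does not remove the point. By-visit SDs would allow a rough unadjusted check, but would leave the reported interval for the Week 4/Week 8 average uncorrected. No planned analysis gives an arm-specific interval for that average.

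**Conclusion.** The concern holds. For a single-arm primary estimate, a by-arm matrix keeps close to 95% coverage over the whole range examined, and a common matrix does so only if the arms have equal spread. The error can go either way, and its actual size cannot be known from the documents. The range of 89.1% to 97.7% rests on an active SD of 7.0 and control SDs of 4 to 9. The significance decision at the planned effect and both between-arm key secondary tests are essentially unaffected. This is a change that should be made, because it is cheap and protects the accuracy of the headline interval. The trial's conclusion does not hang on it.

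**What to change.** In SAP 9.3.1.2, Protocol 12.3.3.1 and the synopsis, state:

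> The within-subject errors will have an unstructured covariance matrix estimated separately for each treatment group (`REPEATED ... TYPE=UN GROUP=treatment`). If this does not converge, one unstructured matrix common to both groups will be fitted; only if that also fails, compound symmetry. Under either fallback, the estimate and 95% CI from a model fitted to the ELX/TEZ/IVA group alone will also be reported.

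- Keep REML and Kenward-Roger.
- The arm-only estimate uses each endpoint's own average: Week 4 and Week 8 for ppFEV₁; Day 15, Week 4 and Week 8 for sweat chloride.
- Apply the same order in SAP 9.3.1.4 with Appendix D (one structure for all 20 imputed datasets), 9.3.1.5, 9.3.2.2, 9.3.2.4, 9.3.3.2 and 9.3.4.2. Flag any fallback in the output.
- Say which result feeds the hierarchical test under a fallback, and make clear that the arm-only estimate is part of 9.3.1.2, so that it does not appear to contradict 9.3.1.3.
- Approve the change as an SAP amendment before database lock and unblinding (SAP 4). If the protocol text is left as it is, record the departure in SAP 3.1.

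**Cost.** Matching text and one SAS option. There are 12 covariance parameters instead of 6, and a slightly higher chance of non-convergence, mainly in small subgroups. In simulation the by-arm model failed in 0 of 18,000 fits at 125 per arm and 1 of 7,400 at 15 per arm; SAS may behave differently. From the simulated half-widths, the primary interval is essentially unchanged at equal SDs. It becomes about 8%, 16% or 24% wider if the control SD is 6, 5 or 4 (1.26/1.17, 1.26/1.09, 1.26/1.02), and about 7% or 13% narrower if it is 8 or 9 (1.26/1.35, 1.26/1.45).

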9.3.1.3 Supportive Analysis

There will be no supportive analysis for the primary efficacy endpoint.

9.3.1.4 Sensitivity Analysis

MMRM based on Multiple Imputation (MI)

An underlying assumption of the MMRM method is that data are missing at random. To minimize the amount of missing data, subjects who prematurely discontinue study drug treatment will continue to complete all scheduled study visits for spirometry and other efficacy assessments.

To assess the impact of missing data and the assumption that data are missing at random, a multiple imputation algorithm will be used if at least 10% of the subjects have missing changes in ppFEV₁ at Week 8 in any treatment group. Missing absolute change from baseline in ppFEV₁ assessments will be imputed starting from the first visit with missing values, for which all subsequent visits through Week 8 are also missing. For intermediate missing data, i.e., missing values that fall between two non-missing ones, it is reasonable to assume that they are missing at random and therefore will not be imputed. An MMRM analogous to that for the primary analysis of the primary endpoint will be applied to each imputed dataset and the relevant MI estimators will be reported. Details for the MI steps are presented in [Appendix D](#).

9.3.1.5 Subgroup Analysis

Subgroup analyses of the primary efficacy endpoint will be performed using a model similar to that of the primary analysis for each of the following subgroups. The primary result obtained from the model will be estimated within-treatment difference through Week 8 (average of Week 4 and Week 8) for the ELX/TEZ/IVA group:

- Age at Screening (<18, ≥18 years)
- ppFEV₁ at baseline (< 70, ≥ 70)
- Comparator group (TEZ/IVA comparator, IVA comparator)
- Sex (male, female)
- Geographic region (North America, Europe)

The MMRM used for the primary analysis will be used for the subgroup analysis, where the same model will be applied to each category of the subgroup. Note that for the subgroup analysis based on comparator group, the covariate of comparator group (TEZ/IVA comparator, IVA comparator) from the MMRM will be removed. The adjusted means with 2-sided 95% confidence intervals will be provided. Furthermore, estimated within-treatment difference through Week 8 (average of Week 4 and Week 8) for the ELX/TEZ/IVA group in different categories within a subgroup will also be presented in a forest plot. Note: The purpose of subgroup analysis is to assess trend consistency; not hypothesis testing with sufficient power. Due to potential small sample size, the results from above mentioned subgroup analysis, especially the comparison between two comparator groups, should be interpreted with caution.

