9 STUDY IMPLEMENTATION

9.1 Study Design

This is a Phase 3, randomized, double-blind, active-controlled, parallel-group, multicenter study (Figure 9-1).

Figure 9-1 VX18-445-104 Study Design

IVA: ivacaftor; ppFEV₁: percent predicted forced expiratory volume in 1 second; SwCl: sweat chloride; TC: triple combination; TEZ: tezacaftor

Note: The Safety Follow-up Visit is not required for subjects who complete the Week 8 Visit and enroll in an open-label study within 28 days after the last dose of study drug.

^a Subjects will be randomized 1:1 to the TC arm or the control arm. Randomization will be stratified based on comparator group (IVA comparator versus TEZ/IVA comparator), ppFEV₁ as determined during the Run-in Period (Day -14 assessment; <70 versus ≥70), and SwCl as determined during the Run-in Period (Day -14 assessment; <30 mmol/L versus ≥30 mmol/L).

Approximately 250 subjects will be enrolled in the study.

- Approximately 40% of total subjects will be in the IVA comparator group (approximately 100 subjects)
 - In the IVA comparator group, up to 20% of subjects may be enrolled with an *R117H* mutation (approximately 20 subjects)
- Up to 15% of total subjects may be enrolled with SwCl values <30 mmol/L at screening (approximately 40 subjects)

Study drug is defined in Section 10.

In the Run-in Period, subjects will be assigned to the IVA or TEZ/IVA comparator group based on genotype per Table 9-1. Subjects assigned to the IVA comparator group will receive

IVA 150 mg every 12 hours (q12h) and subjects assigned to the TEZ/IVA comparator group will receive TEZ 100 mg once daily (qd)/IVA 150 mg q12h.

In the Treatment Period, subjects will be randomized (1:1) to the VX-445/TEZ/IVA treatment arm or control arm under a single randomization scheme. Subjects in the control arm who received IVA in the Run-in Period will receive IVA in the Treatment Period; subjects in the control arm who received TEZ/IVA in the Run-in Period will receive TEZ/IVA in the Treatment Period.

Randomization will be stratified; details are provided in Section 9.2.

The dosages for the Treatment Period are shown in Table 9-2.

Table 9-1 IVA and TEZ/IVA Comparator Group Mutations

IVA Comparator Group Mutations		
R117H	G551D	G1244E
G178R	G551S	S1251N
S549N	G1069R	S1255P
S549R	R1070Q	G1349D
TEZ/IVA Comparator Group Mutations		
711+3A>G	R117C	S977F

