9.1.2 Run-in Period

The Run-in Period has a 4-week duration and is designed to establish a reliable on-treatment (IVA for the IVA comparator group and TEZ/IVA for the TEZ/IVA comparator group) baseline for the Treatment Period. The first dose of open-label IVA or TEZ/IVA (as applicable) will be administered at the Day -28 Visit. The last dose of open-label IVA will be administered in the evening on Day -1 (1 day before the Day 1 Visit).

A subject's screening *CFTR* genotype **must** confirm eligibility before the subject enters the Run-in Period (Section 11.6.2).

On Day -14, spirometry and SwCl will be assessed. The Day -14 spirometry and SwCl assessments will be used for stratification of randomization (Section 9.2).

Subjects who prematurely discontinue study drug treatment during the Run-in Period will not be randomized or participate in the Treatment Period (Section 9.1.5.1) and are not permitted to rescreen.

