9 STATISTICAL ANALYSIS

9.1 General Considerations

The Schedule of Assessments is provided in Section 3 of CSP. The precision standards for reporting safety and efficacy variables are provided in an internal Biometrics document that specifies the programming rules including the precision for derived variables.

Continuous variables will be summarized using the following descriptive summary statistics: the number of subjects (n), mean, standard deviation (SD), median, minimum value (min), and maximum value (max).

Categorical variables will be summarized using counts and percentages. Percentages will be presented to 1 decimal place.

Baseline value, unless otherwise specified, is defined as the most recent non-missing measurement (scheduled or unscheduled) collected before the first dose of study drug in the Treatment Period (i.e., the Day 1 Visit). For ECGs, baseline will be defined as the most recent pretreatment measurement before the first dose of study drug in the Treatment Period (i.e., the Day 1 Visit).

Absolute change from baseline will be calculated as post-baseline value - baseline value.

Relative change from baseline will be calculated as (post-baseline value - baseline value)/baseline value.

The **Treatment-emergent (TE) Period for the Run-in Period** will be from the first dose of study drug in the Run-in Period to (1) the first dose of study drug in the Treatment Period for subjects who complete the Run-in Period and continue to the Treatment Period, or (2) 28 days after the last dose date of study drug in the Run-in Period or to the completion of study participation date, whichever occurs first, for subjects who do not continue to the Treatment Period (e.g., subjects who do not meet the conditions to enter the Treatment Period).

The **TE Period for the Treatment Period** will include the time from the first dose date of study drug in the Treatment Period (TC, placebo + TEZ/IVA, or placebo + IVA) to 28 days after the last dose of the study drug or to the completion of study participation date, whichever occurs first.

Unscheduled visits: Unscheduled visit measurements will be included in analysis as follows:

- 1) In scheduled visit windows per specified visit windowing rules
- 2) In the derivation of baseline
- 3) In the derivation of maximum and minimum values during TE period, and maximum and minimum change from baseline values during TE period for safety analyses
- 4) In individual subject data listings as appropriate

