9.3.2.2 Analysis Method

Absolute change in SwCl from baseline through Week 8 for the ELX/TEZ/IVA group:

Analysis of this endpoint will be based on the same MMRM model as the analysis of the primary efficacy endpoint. Data obtained from the Day 15, Week 4, and Week 8 Visits will be included in the model. Absolute change in SwCl from baseline through Week 8 is defined as average of Day 15, Week 4, and Week 8.

Absolute change in ppFEV₁ from baseline through Week 8 for the ELX/TEZ/IVA group compared to the control group:

Analysis of this endpoint will be based on the same MMRM model as the analysis of the primary efficacy endpoint. Data obtained from the Day 15, Week 4, and Week 8 Visits will be included in the model. However, the Day 15 Visit will not be included in the estimation of the average treatment effect through Week 8.

Absolute change in SwCl from baseline through Week 8 for the ELX/TEZ/IVA group compared to the control group:

Analysis of this endpoint will be based on the same MMRM model as the analysis of the primary efficacy endpoint. Data obtained from the Day 15, Week 4, and Week 8 Visits will be included in the model. Absolute change in SwCl from baseline through Week 8 is defined as average of Day 15, Week 4, and Week 8.

The LS mean (SE) of the within-treatment group change from baseline at each post-baseline visit up to Week 8 along with the 95% CI will be estimated from the corresponding MMRM. The LS mean (SE) of the treatment difference between ELX/TEZ/IVA and control at each post-baseline visit will be provided along with the corresponding 95% CI and *P* value. The LS mean (SE) at each visit will also be plotted by treatment group. In addition, the post-baseline raw values and the absolute change from baseline at each post-baseline visit up to Week 8 will be summarized descriptively (n, mean, SD, median, minimum, and maximum).

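### Efficacy subgroups show only the ELX/TEZ/IVA within-arm ppFEV₁ change; no difference from control is planned by subgroup or by comparator drug

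*SAP*

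**What the plan says.** SAP 9.3.1.5 plans subgroup analyses of the primary endpoint by age, baseline ppFEV₁ (<70, ≥70), comparator group, sex and region. The primary MMRM is reused, "where the same model will be applied to each category of the subgroup", so each fit contains both arms. The named output is one-armed: "The primary result obtained from the model will be estimated within-treatment difference through Week 8", averaged over Weeks 4 and 8 for ELX/TEZ/IVA. The plot is one-armed too: that estimate "for the ELX/TEZ/IVA group in different categories within a subgroup will also be presented in a forest plot". The section adds that "The adjusted means with 2-sided 95% confidence intervals will be provided", without naming the arm. It states that the aim is to look at consistency of trend, and it urges caution because numbers may be small.

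SAP 9.1 defines baseline as the last value before the first Treatment Period dose, and "Absolute change from baseline will be calculated as post-baseline value - baseline value". The baseline ppFEV₁ that assigns a subject to a subgroup is therefore also the value subtracted.

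The between-arm comparison appears in SAP 9.3.2.2 as a key secondary endpoint: "Absolute change in ppFEV₁ from baseline through Week 8 for the ELX/TEZ/IVA group compared to the control group". It covers the whole FAS, with IVA and TEZ/IVA controls pooled. Protocol 12.3.3.1 leaves subgroup analyses to the SAP, and SAP 9.3.1.3 plans no supportive analysis, so no other section supplies a difference by subgroup.

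**The concern.** A within-arm change mixes the drug effect with anything else that moves ppFEV₁ between Day 1 and Weeks 4 to 8. The control arm is there to remove that, and the subgroup display does not use it. This matters most for two of the five factors.

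**Baseline ppFEV₁.** Subjects who happen to blow low on Day 1 are over-represented below 70 and tend to rise afterwards; those who blow high are over-represented at or above 70 and tend to fall. A reader checking whether benefit is consistent across disease severity could see a trend that the drug did not cause. Age, sex and region are not affected in this way.

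**Comparator group.** The run-in is "designed to establish a reliable on-treatment (IVA for the IVA comparator group and TEZ/IVA for the TEZ/IVA comparator group) baseline for the Treatment Period". It aligns the starting point but is not a concurrent control. Whether ELX/TEZ/IVA improves on IVA, and separately on TEZ/IVA, is an obvious clinical question. Comparator group is a randomisation stratum (SAP 7.3), so a properly randomised answer exists in the data, but the plan does not ask for it.

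**Working it through.** **1. The plan's own figure.** SAP 7.2: SD 7.0, effect 3.0, n = 125 with 10% dropout, one-sample t-test, two-sided 0.05. The noncentral t gives 99.4% power at n = 112 and 99.7% at n = 125. The stated >99% reproduces.

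**2. Regression to the mean in the ppFEV₁ subgroups.** Write observed baseline as true value plus error, with error SD σₑ, observed baseline SD σ_b and mean μ. With no drug effect and independent errors,

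expected change in a subgroup = (σₑ²/σ_b²) × (μ − mean baseline in that subgroup).

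The documents give none of μ, σ_b or σₑ; the values below are assumptions. Central case: μ = 67, σ_b = 15, σₑ = 4.

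- Variance ratio: 16/225 = 0.0711.
- Cut point: z = (70 − 67)/15 = 0.2; normal density 0.391; share below 70 is 0.579.
- Mean baseline <70: 67 − 15 × 0.391/0.579 = 56.9. Shift: 0.0711 × 10.1 = +0.72.
- Mean baseline ≥70: 67 + 15 × 0.391/0.421 = 80.9. Shift: −0.0711 × 13.9 = −0.99.
- False gap: 0.72 + 0.99 = 1.71 points.

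A two-arm simulation with a uniform true effect of 3.0 agrees:

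| Baseline ppFEV₁ | ELX/TEZ/IVA change | Control change | Difference |
|---|---|---|---|
| <70 | 3.72 | 0.72 | 3.00 |
| ≥70 | 2.00 | −0.99 | 3.00 |

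Over means 65–68, SDs 13–15 and error SDs 3–5, the gap runs from 0.96 (SD 15, error 3) to 3.13 (mean 65, SD 13, error 5). With error SD 2 it is about 0.4 to 0.5. A separate simulation that imposed the 40–90 screening limits (true between-subject SD 12–15, error SD 2–5) gave 0.5 to 3.4. As a plausibility check, error SD 5 implies an SD of change of 5 × √1.5 = 6.1, inside the planned 7.0.

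**3. Does the baseline covariate remove it?** No. The model is fitted separately in each category, so the adjusted mean is taken at that category's own baseline (assuming the usual evaluation at covariate means). Covariate-adjusted fits with the screening limits imposed still gave 3.78 (<70) and 1.82 (≥70) for ELX/TEZ/IVA under a true effect of 3.0, while the between-arm contrast was about 3.0 in each.

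**4. Cutting on Day −14 instead.** With independent errors the gap is about 0. With serially correlated errors (assumed 0.3 at 14 days, geometric decay) the Day −14 cut leaves 0.45, against 1.63 for the Day 1 cut. The between-arm difference stays within 0.01 of the truth.

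**5. Precision of ELX minus control by comparator group.** Protocol 9.1 puts about 40% of about 250 subjects, roughly 100, in the IVA group, leaving about 150 for TEZ/IVA. With 1:1 allocation, 10% dropout and SD 7.0:

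| Group | Per arm | 95% half-width | Power for 3.0 points |
|---|---|---|---|
| IVA | 50 × 0.9 = 45 | 1.96 × 7 × √(2/45) = 2.89 | 52% |
| TEZ/IVA | 75 × 0.9 = 67.5 | 1.96 × 7 × √(2/67.5) = 2.36 | 70% |

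**The case against.** The primary endpoint is itself a within-arm change, so showing the same estimand by subgroup is consistent, and the lack of a concurrent control is partly a feature of that endpoint. This stands as an explanation. It does not make the display fit for judging consistency of trend when the display can create one.

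The promised adjusted means could include the control arm, in which case a reader could subtract. That reading is possible, but two single-arm means are not a specified difference with a CI.

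The SAP already urges caution. It does so on grounds of sample size, and more subjects would not reduce regression to the mean.

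The strongest point is precision. In the central case about 58% fall below 70, so the within-arm gap between the two ppFEV₁ categories has SE 7 × √(1/65.25 + 1/47.25) = 1.34, a half-width of 2.6, and the 1.7-point artefact lies inside it. Using differences raises the SE to 1.89. By root mean square error the within-arm gap is better when the artefact is below about 1.34; in the central case it is worse, √(1.71² + 1.34²) = 2.17 against 1.89. This trade-off is real. It argues for showing both quantities, which costs no precision, and not for omitting the difference.

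**Conclusion.** The concern holds. For every efficacy subgroup the SAP specifies and plots only the ELX/TEZ/IVA within-arm change, and no ELX-minus-control estimate by subgroup or by comparator drug is planned anywhere in the protocol or SAP.

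The direction of the ppFEV₁ tilt follows from the design. Its size depends on variances the documents do not give: 1.7 points in the central case and 1.0 to 3.1 for error SDs of 3 to 5, lower if spirometry is more repeatable than that, set against a planning effect of 3.0. By-comparator differences would be imprecise, at about ±2.9 and ±2.4 points, and should be read as estimates only. The primary and key secondary tests are unaffected. This is a change the plan should make, not one on which its validity depends.

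**What to change.** In SAP 9.3.1.5, for each category of each subgroup, add the ELX-minus-control difference in ppFEV₁ through Week 8 (average of Weeks 4 and 8) with its 95% CI from the model already fitted. Plot it beside the within-arm change and label it descriptive. State that within-arm changes in the baseline ppFEV₁ categories are subject to regression to the mean.

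Optionally, group the within-arm ppFEV₁ display by the Day −14 stratum. This is unnecessary once the difference is shown, and it removes the bias fully only if Day −14 and Day 1 errors are independent.

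The cost is one extra contrast per model and one extra forest-plot column. No new data, visits or alpha are needed.
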